2.6 Data collection timelines

After the approval of the protocol from the participating registries and the expert partners involved in the study, we expect to collect the information within approximately 10 months, commencing from 1st July 2021. Due to the length of time to finalise the Data Transfer Agreement (DTA) with the large number of participating PBCRs, the timeline has been extended.

A centralised desk for information will be available at the INT Milan ([contact]) or [name] and [name] e-mail.

The final deadline for transmitting data, including final follow up data, to the INT is November 2022.

2.7 Quality checks

Data files will be checked with ad hoc developed procedures in regular use at the INT. For each tumour record, the validity of each variable, and of combinations of different variables (such as dates sequence, or ICD-O morphology and topography codes combinations, etc), will be checked to detect wrong/unlikely values. The already existing JARC pilot study quality checks procedures will be updated to incorporate the newly included cancers.

The records flagged by the data checking process will be sent back to the registries for their revision/correction/confirmation. The INT portal will be used for these transmissions to and from the registries. This data quality checking process is the reason for retaining a pseudonymised link for each record, that can only be decoded by the cancer registry that submitted the record.

Cases ascertained only by the death certificates (DCO), number of cases diagnosed by cytology or histology (MV) and those with unspecified morphology codes (NOS) will be considered as data quality indicators for the diagnosis. The number of cases lost to follow-up and the number of those censored before the date of end of follow-up will be calculated and considered for the definition of quality of follow-up.

2.8 Statistical considerations

The main endpoints for the statistical analyses, by tumour type, are:

1. Differences in stage distribution between countries/regional groupings.
2. Survival differences between countries/regional groupings, and how much of any difference is explained by variations in stage distribution and/or survival by stage.

The formal statistical power to detect differences in stage distribution and survival rates between countries is necessarily limited by incident numbers of each of the six tumour types per country over the recent time period for which PBCRs are able to provide tumour stage. Therefore, analyses of stage distribution and survival rates for each tumour type per country will be descriptive, with 95% confidence intervals reported.

Approximately 8,000 cases will be included (table 2). As the study is population-based, these are the largest numbers available and are not biased in the ways that might affect institutional or clinical trial series.

Endpoint 1: To formally assess if differences in tumour stage at diagnosis are significant, we will group European countries according to the regional geographies used in EURO CARE 5 to achieve the group sizes necessary. Non-European jurisdictions will be considered individually. For expected case numbers by registry (table 2), we have approximately 60% power to detect a 10% difference in lower stages (localised, loco-regional) versus more advanced stage (metastatic) between two countries or regional groupings where there are 250 cases of each tumour type in each group (medulloblastoma, Wilms tumour). For group sizes with 300 cases (neuroblastoma), the power would be 70%. We will combine the sarcomas, who collectively comprise 29% of the cohort, for assessment of differences in stage distribution at diagnosis, according to the same country groupings.

Endpoint 2: Overall survival for each tumour type will be analysed for all patients and broken down by appropriate tumour stage, using standard Kaplan-Meier methods reported with 95% CIs. Survival differences between countries/regional groupings and how much is explained by variations in stage distribution will be studied by multivariable Cox regression including stage and other relevant prognostic variables (age at diagnosis, sex and/or primary site for at least some diagnostic groups), and confounders including stage migration.

3. Oversight and funding of the project

Day to day management of the project will be performed jointly by [name] (assisted by [name]) – Head of the Evaluative Epidemiology Unit, INT, Milan, and [name] – Paediatric oncologist, University College London, UK. The more detailed project management plan is described in section 6.

Colleagues who led the development of the Toronto consensus staging guidelines have already developed an operational manual for their application that they have agreed to share with us and welcome our input into their further iteration as they are applied more widely. The manual has been translated from English to French, Italian, Portuguese and Spanish language and will be available to the registrars.

Webinars will be organized to disseminate and discuss the protocol. The European School of Oncology has already led two events and the recorded seminars are available on the web (see above). Further courses will be organized during 2021. An Italian initiative involving the Italian registries was held in February 2020 in Palermo and further national initiatives will be encouraged. Registries from the European regions speaking Latin languages (GRELL collaborative initiative, 2019-2020) will organise seminars/courses/workshop in their spoken languages.

The main funding for the project is provided by a peer-reviewed competitively awarded project grant from Children with Cancer UK (<https://www.childrenwithcancer.org.uk/childhood-cancer-info/we-fund-research/projects-we-fund/understanding-why-childhood-cancer-survival-varies-between-countries/>). This award includes a modest sum (estimated about £11 per case) for reimbursement to participating cancer registries for their efforts in sourcing and providing the Toronto staging data for the project. [name] is the Principal Investigator, [name] is a named Co-Investigator. [name] is responsible for reporting to the funder. [name] has obtained additional funds to support participation of the Italian cancer registries.

4. Ethical approval, research governance and GDPR compliance (confidentiality and data processing)

Ethical approval for the project has been given by the Research Ethics Committee of University College London on 22nd April 2021 and is valid until 30th June 2024. Also, the Ethical Committee of the Fondazione IRCCS “Istituto Nazionale dei Tumori” approved the project during the e-session on 25th May 2021.

A copy of the UCL REC approval letter is included in the appendix.

Additional approvals that may be required at the national or regional level by the other participating PBCRs will be requested from their applicable competent ethical or regulatory authorities, according to national regulations. If a PBCR needs a Data Transfer Agreement – a formal contract that clearly documents what data are being transferred and how the data can be used – it will be stipulated, agreed and signed directly between the parties (INT and each CR). Please write a formal request by email to [contact], describing the requirements of your cancer registry and the name of the legal /administrative contact in your institution. This process will facilitate the contact with the legal entity of the Fondazione IRCCS “Istituto Nazionale dei Tumori” of Milano who will provide a template for the agreement.

Participating PBCRs will be responsible for ensuring these approvals are in place and for their collection and sharing of detailed pseudonymized clinical data according to the rules that ensure patient confidentiality, and which are GDPR-compliant. This includes having the responsibility of Data Controller for the data they submit to the project.

The BENCHISTA Project Working Group includes representation from all PBCRs contributing data to the project, as well as tumour-specific clinical leads from the relevant European clinical trials groups, parent and patient representation and the principal investigators at UCL and INT, Milan. The format of the data items to be collected has been agreed with the PBCRs to be in the maximally de-identified format that minimises any risks to data privacy, in compliance with GDPR. UCL and INT will act as joint Data Controllers for the project, with responsibilities as defined by article 26, GDPR and with the legal basis for data processing under article 6, GDPR 2018 being “Public interest” (clause (e)) and article 9 par.2 clause (j) and (i)“pub; art. 12 of DIRECTIVE 2011/24/EU;article 168, p.2, of Treaty on the Functioning of the European Union. Only INT has access to pseudo anonymised personal data and UCL does not.

The INT rules for the management of the project data base will be used for the analyses:

- 1- INT will receive pseudo-anonymised records from registries in xlsx format (; as delimiter).
- 2- Data will be transferred to INT using the secure platform *Microsoft SharePoint* or any other secure platform required by the PBCRs to comply with their data protection laws.
- 3- The database will be part of the INT computer system, and its storage and access will follow the rules already adopted by INT (see appendix for Data safety details).
- 4- Only personnel authorized and involved in the project will access the database based in Milan.
- 5- Database will be managed in Excel and then Stata used for the analyses.
- 6- The analyses will cover the objectives of the project and possible related issues.
- 7- The analyses may last at least 5 years if further follow up information is available and/or to address any queries from referees during submission of project manuscripts for peer reviewed publication.

- 8- After 10 years from project initiation (i.e., January 2031), the database will be deleted unless further requests for data analysis have been requested and the necessary approval obtained from the data providers and the project governance approvers of UCL and INT.

The BENCHISTA data remain the property of the contributing registries, whose consent is required before they can be used for purposes other than those originally envisaged in the BENCHISTA protocols. All members of the Working Group that provide data must be informed of any analysis being carried out.

PBCRs will send the dataset to the analytical team at the epidemiology research group in the National Tumour Institute, Milan, Italy, who will check the quality data, calculate and compare stage at diagnosis and survival rates between countries. The association between variation in tumour stage and survival differences will be tested. Further variables such as NSP and recurrences will be evaluated and may be used in analyses according to their completeness.

This document (BENCHISTA Final Protocol, version 4.4) should be used as the final protocol describing the work to be undertaken to assess the feasibility of applying the Toronto staging guidelines on population-based cancer registry data and organising the collection of tumour stage by European cancer registries in a routine way.

The list of the procedures for security measures (both technical and organizational) implemented at the INT are summarized in the appendix.

5. Outcome and Publication Policy

The main output from this project will be the publication of stage distribution and survival by stage for childhood cancer patients. Geographical differences will be presented by (large) country or, depending on sample size, by geographical region. This will maximise statistical robustness and will minimise the risks to data privacy. Analyses according to other major variables such as recurrence, treatment and NSP will be considered according to the completeness of these variables.

6. Project Management

One participant for each contributing registry will be member of the overall Project Working Group (PWG). PBCRs contributing more than 50 cases will identify two persons to be included in the PWG. It is the population-based cancer registry directors' responsibility to define the PWG member for each PBCR and to inform the project leaders regarding the correct email contact for their participants. In addition, a lead oncologist for each tumour type will be nominated from the relevant tumour-specific European clinical trial groups.

This PWG will finalise the detailed data collection and analysis protocol, obtain ethical approval in each country and support each registry in accessing the necessary data linkage from clinical registries and routine hospital information systems. PWG members will receive regular updates on the project's progress and will always be included as a named working group in each publication regarding the project. This group will convene quarterly online. All PWG members will be able to make the most of the capabilities of this database; if a member of the working group has a new paper proposal that could use the project database, it will be circulated with the PWG. If no negative feedback comes back from the Project Management Team (PMT) within one month, this will be taken as a positive reply from all the registries.

The PMT comprises the research leaders in the UK and Italy with a smaller number of nominated representatives from the PWG. This will convene bi-monthly throughout the project (Table 1 and Figure 1).

Table 1. Project Management Team

PMT members	Country	Affiliations
[name]	UK	UCL Great Ormond Street Institute of Child Health, University College London, UK
[name]	Italy	Research Department, Fondazione IRCCS Istituto Nazionale dei Tumori, Milan, Italy
[name]	Italy	Research Department, Fondazione IRCCS Istituto Nazionale dei Tumori, Milan, Italy

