2.2 Inclusion criteria

The updated ENCR (European Network of Cancer Registries) recommendations (<https://encr.eu/sites/default/files/pdf/incideng.pdf>) should be followed to record the date of incidence used by the registry to define their cases meeting the inclusion criteria.

- Cases to be included are all children aged <15yrs with the relevant histology codes (detailed in the Appendix that describes the Toronto staging systems for each tumour type). For the three cancer types that are common in adolescents (osteosarcoma, Ewing sarcoma and rhabdomyosarcoma), cases aged 15 -19 (inclusive, i.e., < 20) years of age will be included if data are held by the registry.
- Cases must be diagnosed between 01.01.2014 – 31.12.2017, one year incidence back and forth will be considered in order for a registry to have a minimum of three consecutive years' worth of cases, providing 3 years follow-up is assured.
- All consecutive incident cases must be identified and submitted by each PBCRs.
- Cases should have at least 3 years of follow-up for the definition of the life status, according to PBCR practice.
- After an agreement with the INT team, follow up data could be submitted separately and at a later timepoint during the second year of the project, to allow for maximum follow-up on all patients.

Cases with problems in the definition of stage because of scarcity of information must be included and not eliminated.

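### The formal sarcoma stage comparison pools three tumours over registry-dependent age ranges with no tumour or age stratum stated, so differences in age coverage and tumour mix can be read as stage differences

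*Protocol*

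**What the plan says.** Section 2.8 of the protocol introduces its endpoints with "The main endpoints for the statistical analyses, by tumour type, are". Results per country are to be non-inferential: "analyses of stage distribution and survival rates for each tumour type per country will be descriptive, with 95% confidence intervals reported". The formal step works on regions: "To formally assess if differences in tumour stage at diagnosis are significant, we will group European countries according to the regional geographies". Non-European jurisdictions stand alone. The three sarcomas are then merged for that step: "We will combine the sarcomas, who collectively comprise 29% of the cohort, for assessment of differences in stage distribution at diagnosis". No test, covariate or stratum is named for Endpoint 1.

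The ages entering that comparison are not uniform. Section 2.2 makes the older sarcoma patients conditional: "cases aged 15 -19 (inclusive, i.e., < 20) years of age will be included if data are held by the registry". Table 3 heads the sarcoma columns 0-19 years but footnotes the German sarcoma counts as 0-17.

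Age adjustment appears once, in the Endpoint 2 Cox model, which includes "other relevant prognostic variables (age at diagnosis, sex and/or primary site for at least some diagnostic groups").

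**The concern.** Hypothesis 1 in section 1 treats a regional difference in advanced stage as possible evidence of late diagnosis and as a target for intervention. The sarcoma contrast should therefore reflect stage, not who was counted.

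Three things can distort it:

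- **Age coverage.** If one region includes ages that another does not, and metastatic share depends on age, the contrast carries the age difference.
- **Tumour mix.** If metastatic share differs between the three sarcomas, regions with different mixes differ even when every tumour-specific share is equal.
- **Dilution.** A real difference in one sarcoma is averaged with two tumours that show none.

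The protocol fixes the pooling itself, and it sits awkwardly under endpoints stated by tumour type.

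**Working it through.** **1. The plan's own figures.** Section 2.8 states "we have approximately 60% power to detect a 10% difference in lower stages (localised, loco-regional) versus more advanced stage (metastatic") with 250 cases per group, and "For group sizes with 300 cases (neuroblastoma), the power would be 70%". For two proportions, two-sided alpha 0.05 (assumed), pooled variance under the null:

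power = Φ{[Δ − 1.96·√(2p̄(1−p̄)/n)] / √([p1(1−p1)+p2(1−p2)]/n)}

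With Δ = 0.10 and baselines of 40-50%, this gives 60.9-61.4% at n = 250 and 68.9-69.3% at n = 300. Both figures reproduce. At a 25% baseline they would be 68.5% and 76.3%. The 29% does not reproduce: the printed rows of Table 3 give 3,449/9,498 = 36.3% sarcomas. That is a side matter here.

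**2. Age coverage.** The protocol gives no count aged 15-19. A rough indicator is R = expected sarcomas / expected 0-14 tumours (embryonal CNS + neuroblastoma + renal), from Table 3.

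| Group | Sarcomas | 0-14 tumours | R |
|---|---|---|---|
| England | 412 | 596 | 0.69 |
| Netherlands | 157 | 214 | 0.73 |
| Germany (0-17) | 511 | 852 | 0.60 |
| France | 410 | 962 | 0.43 |
| Australia | 156 | 339 | 0.46 |
| Japan | 61 | 182 | 0.34 |
| UK and Ireland | 550 | 785 | 0.70 |
| Central | 1,307 | 2,366 | 0.55 |

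The protocol does not list the regions. Central is assumed to be Austria, Belgium, France, Germany, the Netherlands and Switzerland.

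**3. Size of the age artefact.** If R differs only through age coverage, the share of one group's sarcomas from ages the other lacks is s = 1 − R(low)/R(high). The spurious gap is s × δ, where δ is the difference in metastatic share between 0-14 and 15-19. The protocol gives no δ; 5-10 points is assumed.

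- UK and Ireland vs Central: s = 1 − 0.552/0.701 = 0.21, so the gap is 0.21 × 5 to 0.21 × 10, about 1-2 points. At a 25% metastatic share (assumed), SE = √(0.25 × 0.75 × (1/550 + 1/1,307)) = 0.022. A 1-point gap is then rejected about 7% of the time and a 2-point gap about 15%, instead of 5%.
- Australia vs UK and Ireland: s = 1 − 0.460/0.701 = 0.34, gap 1.7-3.4 points.
- Japan vs UK and Ireland: s = 1 − 0.335/0.701 = 0.52, gap 2.6-5.2 points, on only 61 sarcomas.

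**4. Tumour mix.** Ewing is 140/550 = 25.5% of sarcomas in UK and Ireland and 379/1,307 = 29.0% in Central. With assumed metastatic shares of 20/30/20% (osteosarcoma, Ewing, rhabdomyosarcoma), the gap is 0.035 × 10 = 0.35 points. Across countries with at least 100 expected sarcomas, and assumed shares of 10-40%, the largest gap is 0.9-2.8 points.

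**5. Dilution.** Overall sarcoma shares are 1,168, 1,005 and 1,276 of 3,449, i.e. 33.9%, 29.1% and 37.0%. A 10-point difference in one tumour only becomes 3.4, 2.9 or 3.7 points pooled. At 250 pooled cases per group and a 25% baseline, power is 11-15% pooled, against 26-32% in that tumour alone (73-92 cases per group).

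For UK and Ireland vs Central, take metastatic shares of 20/25/20% or 20/30/20% and add 10 points to Ewing in UK and Ireland. Power is 18-21% pooled (550 vs 1,307) and 58-61% in Ewing alone (140 vs 379).

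**6. Cost of stratifying by tumour.** For a common 10-point difference at 250 per group, crude vs Mantel-Haenszel power is 60.9% vs 60.9% (all baselines 45%), 70.4% vs 70.8% (20/30/20%) and 70.9% vs 74.1% (10/40/20%).

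**The case against.** The strongest reply has four parts.

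*Tumour-specific results are kept.* This stands. Section 2.8 retains descriptive stage distributions per tumour and country with 95% CIs, and Kaplan-Meier is run per tumour. A reader might infer that a difference confined to one sarcoma would go unreported. It would not; it would only lack a formal regional comparison.

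*Stratification belongs in the SAP.* This stands in part. The protocol does not prescribe a crude table, and an SAP could add strata. But the protocol itself fixes the pooling and the registry-dependent age range, and it names age for one endpoint only.

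*The ratios do not establish age coverage.* This stands. One might read Table 3 as showing that France or Japan supplies only 0-14. Only Germany is footnoted, and R also varies among rows labelled simply National: Finland 32/68 = 0.47, Bulgaria 52/63 = 0.83. The counts are expectations, mostly from 2005-2013. England against France would imply s = 0.38 and 2-4 points, but the formal European comparison is between regions, where s is about 0.21.

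*Separate tests or a 0-14 restriction are not free.* This also stands. Three tests of small tumours are underpowered. If France's Ewing ratio (113/962) represented 0-14, restriction would cut Ewing from 140 vs 379 to about 92 vs 278, and power from 61% to about 46% (25% baseline).

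**Conclusion.** The point holds in a limited form. The only formal sarcoma stage comparison merges three tumours over age ranges that depend on the registry. It states no tumour or age stratum, under endpoints defined by tumour type.

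For the regional contrast examined, the age artefact is about 1-2 points against a 10-point target, with false rejection of about 7-15% rather than 5%. It can be larger for jurisdictions taken individually. Tumour mix adds little. Dilution of a single-tumour difference to about 3-4 points is arithmetic.

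The age figures rest on an assumed 5-10 point difference in metastatic share by age, an assumed regional grouping, and the reading of Table 3 ratios as age coverage. Only Germany's departure from 0-19 is documented. It would be too strong to say that age and case mix will appear as stage differences: they can, if coverage differs between groups and metastatic share varies by age or tumour. Should-fix, moderate confidence.

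**What to change.** Amend Endpoint 1 in section 2.8 as follows:

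- Keep the combined sarcoma test, but stratify it by tumour type and age band (0-14, 15-17, 18-19), using Mantel-Haenszel or logistic regression. A stratum to which only one group contributes then carries no weight in the contrast.
- Add a region-by-tumour heterogeneity check and report regional stage distributions for each sarcoma with 95% CIs. Stratifying removes confounding by tumour mix but still averages a one-tumour effect, so this part addresses dilution.
- Give a 0-14 analysis as a sensitivity analysis for the sarcoma stage and Kaplan-Meier comparisons.

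Age in months and morphology are already compulsory, so no new data are needed. The tumour stratification costs no material power. The price is slightly more analysis work and lower precision in the 0-14 sensitivity analysis.

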Application of this standardised way to collect stage and a complete collection of stage at diagnosis on all cases by cancer registries is necessary for comparison and interpretation of any outcome differences in population-based analyses. It should be emphasised that Toronto staging is not used as a clinical instrument for choosing a treatment – this is done using risk stratification criteria defined by the treatment protocol applied to an individual patient and which may vary between countries and treatment centres. The importance of the Toronto staging is as a tool for cancer registries to have comparable stage information at a population-level for each of the commonly recognised childhood cancers.

The broad aims of this project are to improve understanding of the reasons for variation in childhood cancer survival between countries and to highlight areas to be targeted for improvement. Tumour stage is a determinant of the likelihood of cure and the intensity of treatment required by the cancer patient. We aim to stimulate the application of the TG by the greatest number of European PBCRs, for the most common solid paediatric cancers. The collection should be in a routine way, that is stage should be included as a mandatory variable. To do this and for conducting in a sustainable way future outcomes research, closer working relationships between PBCRs, clinical services and tumour-specific clinical study groups should be stimulated.

The specific hypotheses to be tested are:

- 1: Are childhood cancers diagnosed at a more advanced stage in some countries compared to others?
- 2: Do survival rates by tumour stage vary between countries/large geographic regions?

Hypothesis 1 assesses if evidence exists for late diagnosis of cancer in children in some countries. If significant differences are found in the proportion of children diagnosed with more advanced stage tumours, this may be

due to differences in awareness of childhood cancer signs and symptoms (by parents/public and community healthcare workers), or to differences in child health systems for routine surveillance and primary care, or to delays after referral to secondary care. All are potential targets for future interventions.

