Hypothesis 2 assesses if evidence exists for variation in survival rates for the same tumour type and stage between countries/regions. If differences are found, this may be due to differences in diagnostic and treatment practices, tumour biology or supportive care. The project will test how well PBCRs can collect data on these items and relapse, so that these further hypotheses can be tested.

These questions will be addressed through the following activities:

1. Participating PBCRs will assign tumour stage at diagnosis at a population level for six specified childhood solid tumours, using the “Toronto” staging guidelines [5,8,9].
2. Participating PBCRs will share a pseudonymised patient-level dataset with the central data analysis team in Milan, including additional variables (feasibility study) where available (non-stage prognosticators, summary of primary treatment, any relapse and cause of death).
3. Comparative analysis of distribution of tumour stage at diagnosis at a population level.
4. Analysis of overall survival by stage for each tumour type, with comparisons between sufficiently large population groups (country-level or European region) for statistically powered analysis of variation and avoidance of reidentification of included cases.
5. Production of practical recommendations on strengthening joint working between PBCRs and clinical/hospital registries so that staging of newly diagnosed childhood cancer patients becomes more efficient and complete. This will allow the analysis of survival by stage to be performed in a sustainable way using routine health care data for prospective clinical observational studies in the future.

The cooperation of PBCRs with clinical/hospital data bases will also assess how easily PBCRs can collect data on first line treatment, tumour biology, non-stage prognosticators (NSP) [9] relapse and cause of death. This feasibility aspect of the project will evaluate how well PBCRs can collect these variables. This information will form the basis for development of future studies that would utilise these data items to explore in more depth the underlying reasons for any variation in survival rates. Collection of these variables will also stimulate collaboration between clinicians in charge of clinical/hospital data bases and registries and their corresponding national/regional population-based cancer registries.

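### Endpoint 2 asks how much of a regional survival difference stage explains, but the Cox regression named for it does not yield that share

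*Protocol*

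**What the plan says.** The second main endpoint in protocol section 2.8 covers survival differences between countries or regional groupings and "how much of any difference is explained by variations in stage distribution and/or survival by stage". It therefore asks for a split into two components. Hypothesis 2 in section 1 asks "Do survival rates by tumour stage vary between countries/large geographic regions" and is explained there as "variation in survival rates for the same tumour type and stage between countries/regions".

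Two methods are named for Endpoint 2 in section 2.8:

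- Overall survival per tumour type, "broken down by appropriate tumour stage, using standard Kaplan-Meier methods reported with 95% CIs".
- A regression: "Survival differences between countries/regional groupings and how much is explained by variations in stage distribution will be studied by multivariable Cox regression including stage", together with age, sex, primary site for some tumours, and stage migration as a confounder.

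Two further statements matter. Activity 4 in section 1 announces "Analysis of overall survival by stage for each tumour type, with comparisons between sufficiently large population groups (country-level or European region", without naming a test. Section 2.8 also says that "analyses of stage distribution and survival rates for each tumour type per country will be descriptive, with 95% confidence intervals reported".

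The sentence that assigns the Cox model mentions only the stage-distribution component; the survival-by-stage component of the endpoint is not repeated there. No quantity is defined for the share explained.

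**The concern.** The endpoint is a proportion: what part of a regional survival gap comes from later stage at diagnosis, and what part from worse survival at the same stage. Section 1 ties these to different causes. Stage distribution points to awareness, primary care and referral. Within-stage survival points to diagnosis, treatment, tumour biology and supportive care. A distorted split would send attention to the wrong place.

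Cox regression gives hazard ratios, not a share. An analyst told to obtain the share from this model would most naturally see how far the regional log hazard ratio moves when stage is added. That movement mixes two things: real differences in stage mix, and the change that occurs whenever a strong prognostic factor is added to a Cox model. In the worse region, patients with metastatic disease die sooner, so its survivors become progressively lower-risk and the unadjusted hazard ratio is pulled towards 1. Adding stage undoes this even if the two regions have the same stage mix.

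Separately, one stage-adjusted regional hazard ratio averages over stages. It does not say whether a deficit lies in localised disease, metastatic disease or both.

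**Working it through.** **The protocol's own figure.** Section 2.8 gives power only for Endpoint 1: about 60% for a 10-point stage difference at 250 per group, and 70% at 300. With a two-sided 5% test (assumed, as is the base proportion) and 45% against 55%:

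- n = 250: SE under the null = √(0.5/250) = 0.0447; SE under the alternative = √(0.495/250) = 0.0445; power = Φ[(0.10 − 1.96 × 0.0447)/0.0445] = 0.609.
- n = 300: the same formula gives 0.689.

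Both figures reproduce. They do not bear on Endpoint 2, but they supply the group sizes used below.

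**Inputs for Endpoint 2.** Follow-up is 3 years (the minimum in section 2.2). All survival rates and stage shares are assumptions, because the protocol gives none. There are two regions (A, B), two stages (L localised, M metastatic) and constant hazards within stage. Cox fits used 200,000 simulated cases per region, so sampling error is about 1 to 3 percentage points.

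**Measures.**

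- Log-HR share = (ln HR crude − ln HR adjusted)/ln HR crude.
- Crude difference Δ = S_A − S_B in 3-year survival.
- Standardised difference Δ_std = Σ w_s (S_As − S_Bs), with w_s a common stage mix.
- Stage share = (Δ − Δ_std)/Δ.

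Example, case 3. In A, L and M survival are 0.90 and 0.50, with 30% metastatic. In B, 0.90^1.3 = 0.872 and 0.50^1.3 = 0.406, with 40% metastatic.

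- S_A = 0.7 × 0.90 + 0.3 × 0.50 = 0.780.
- S_B = 0.6 × 0.872 + 0.4 × 0.406 = 0.686.
- Δ = 0.0944.
- Pooled mix 35%: Δ_std = 0.65 × 0.0280 + 0.35 × 0.0939 = 0.0511; share = (0.0944 − 0.0511)/0.0944 = 46%.
- Region A's mix as standard: Δ_std = 0.7 × 0.0280 + 0.3 × 0.0939 = 0.0478; share = 49%.
- Log-HR share = (ln 1.531 − ln 1.300)/ln 1.531 = 38%.

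Case 3b uses 0.95 and 0.30 in A, hence 0.9355 and 0.2091 in B. Here Δ = 0.1101 and pooled Δ_std = 0.65 × 0.0145 + 0.35 × 0.0909 = 0.0413, so the share is 62.5%.

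| Case | Metastatic A / B | Crude HR | Adjusted HR | Log-HR share | Δ | Stage share (pooled mix / A's mix) |
|---|---|---|---|---|---|---|
| 1: same mix, within-stage HR 1.5 | 30 / 30% | 1.42 | 1.49 | -15% | 0.076 | 0% |
| 1b: same mix, stronger stage effect, HR 2 | 30 / 30% | 1.51 | 1.99 | -67% | 0.096 | 0% |
| 2: mix only | 30 / 40% | 1.21 | 1.00 | 103% | 0.040 | 100% |
| 3: mix plus HR 1.3 | 30 / 40% | 1.53 | 1.30 | 38% | 0.094 | 46% / 49% |
| 3b: as 3, stronger stage effect | 30 / 40% | 1.57 | 1.30 | 43% | 0.110 | 62.5% / 66% |

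The 103% in case 2 is simulation noise around 100%.

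**What one adjusted hazard ratio shows.** With 30% metastatic in both regions:

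- Metastatic-only deficit (3-year survival 60% against 45%; localised 90% in both): adjusted HR 1.35, made up of 1.00 in L and 1.56 in M.
- Opposite directions (L 92% against 86%, M 48% against 58%): adjusted HR 1.01, made up of 1.82 in L and 0.74 in M.

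**Power at 250 (300) per group**, 1,000 replicates:

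| Truth | Stage-adjusted region effect | Region-by-stage interaction | Joint test of region across stages |
|---|---|---|---|
| HR 1.5 in every stage | 0.62 (0.73) | 0.04 (0.05) | 0.52 (0.64) |
| Metastatic only | 0.32 (0.39) | 0.18 (0.21) | 0.37 (0.45) |
| Opposite directions | 0.04 (0.05) | 0.53 (0.66) | 0.46 (0.57) |
| Stage mix only, 30 / 40% | 0.04 (0.04) | 0.04 (0.05) | 0.05 (0.04) |

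**The case against.** The strongest reply is that the protocol neither restricts the Cox model to main effects nor says the share will be read from a change in hazard ratio, and that interaction terms and decomposition measures are commonly left to a statistical analysis plan. This is correct as a reading: both are inferences. What remains is that section 2.8 does choose the method for this endpoint, and the chosen method does not produce the quantity that the endpoint defines.

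A reader might go further and infer that the plan cannot test whether survival by stage differs between regions. The documents do not support that. The region coefficient given stage validly tests a common within-stage difference (power 0.62 to 0.73 at HR 1.5, and about 0.04 under the null).

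A reader might also infer that a deficit confined to one stage would go unseen. That does not follow either: Kaplan-Meier estimates by stage with intervals are planned, and activity 4 announces by-stage comparisons between large groups. These would display such a deficit, though no test or summary measure of it is named.

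Lastly, part of the gap in cases 3 and 3b arises from comparing a share on the log-hazard scale with one on the survival-probability scale. That is fair. It does not apply to cases 1 and 1b, where stage mix is identical and the share due to mix is zero on any scale.

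**Conclusion.** The point holds as a mismatch between endpoint and method. Endpoint 2 asks for a quantified attribution, the Cox regression named for it does not supply one, and its natural reading misstates the stage share whenever within-stage survival differs, which is the situation that hypothesis 2 is about. The size depends on the assumed rates: -15% to -67% against a true 0% with identical mix and a uniform within-stage deficit, 38% to 43% against 46% to 66% with both causes present, and no material error when only stage mix differs. The direction of error was the same across the assumed stage effects; the exact figures should not be carried over to any one tumour.

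On hypothesis 2 the gap is narrower. A common within-stage difference is tested; whether the difference varies by stage is left to description. The change is worth making before analysis, but the planned Cox and Kaplan-Meier analyses remain useful and no data are lost.

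**What to change.** Keep the Cox model and the Kaplan-Meier estimates, and add two definitions to section 2.8.

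1. **Share explained by stage.** For each tumour type and pair of regional groupings, report the crude difference in 3-year survival, the difference after direct standardisation of both regions to the pooled stage (and age) distribution, and the gap between the two as the part due to stage, each with a bootstrap confidence interval. Report the share only alongside these differences, since a ratio is unstable when the crude difference is small.
2. **Hypothesis 2.** Report region effects within each stage with confidence intervals, and a joint test of region across stages (region plus region-by-stage terms). Keep the interaction test as secondary: with a uniform deficit of HR 1.5 its power is only 0.04 to 0.05, so it would miss a case in which hypothesis 2 is plainly true.

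Stage, age and follow-up time are already compulsory items and 3 years of follow-up is already required, so no new data are needed. The cost is wording and modest programming. The joint test gives up some power against a uniform deficit (0.52 against 0.62 at 250 per group, 0.64 against 0.73 at 300). Within-stage and interaction estimates will be imprecise at 250 to 300 cases per group, so they should be read mainly as estimates with intervals.
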